8.0 PHARMACEUTICAL INFORMATION

8.1 Atezolizumab (Tecentriq)

8.1.1 Atezolizumab Description

Atezolizumab is a humanized IgG1 monoclonal antibody consisting of two heavy chains (448 amino acids) and two light chains (214 amino acids). Atezolizumab targets human PD-L1 and inhibits its interaction with its receptor PD-1. Atezolizumab also blocks the binding of PD-L1 to B7.1, an interaction that is reported to provide additional inhibitory signals to T cells (Butte et al. 2007).

8.1.2 Clinical Pharmacology

PD-L1 may be expressed on tumor cells and/or tumor infiltrating immune cells and can contribute to the inhibition of the anti-tumor immune response in the tumor microenvironment. Binding of PD-L1 to the PD-1 and B7.1 receptors found on T cells and antigen presenting cells suppresses cytotoxic T-cell activity, T-cell proliferation and cytokine production.

Atezolizumab is a monoclonal antibody that binds to PD-L1 and blocks its interactions with both PD-1 and B7.1 receptors. This releases the PD-L1/PD-1 mediated inhibition of the immune response, including activation of the anti-tumor immune response without inducing antibody dependent cellular cytotoxicity. In syngeneic mouse tumor models, blocking PD-L1 activity resulted in decreased tumor growth.

8.1.3 Pharmacokinetics and Drug Metabolism

Patients' exposure to atezolizumab increased dose proportionally over the dose range of 1 mg/kg to 20 mg/kg, including a dose of 1200 mg administered every 3 weeks. The clearance (CV%) was 0.20 L/day (29%), the volume of distribution at steady state was 6.9 L, and the terminal half-life was 27 days. Steady state was achieved after 6 to 9 weeks following multiple doses. The systemic accumulation ratio for every 2 weeks administration and every 3 weeks administration was 3.3- and 1.9-fold, respectively. Atezolizumab clearance was found to decrease over time, with a mean maximal reduction (CV%) from baseline value of approximately 17% (41%); however, the decrease in clearance was not considered clinically relevant.

8.1.4 Supplier

Atezolizumab is provided by Genentech.

8.1.5 Dosage Form and Preparation

The atezolizumab 840 mg drug product will be supplied in a single-use, 15-mL USP/Ph. Eur. Type 1 glass vial as a colorless to slightly yellow, sterile, preservative-free clear liquid solution intended for IV administration. The vial is designed to deliver 14 mL (840 mg) of atezolizumab solution, but may contain more than the stated volume to enable delivery of the entire 14-mL volume. Patients will receive 1680 mg of atezolizumab, so 2 vials will be used for each dose.

The prescribed dose of atezolizumab should be diluted in 250 mL 0.9% NaCl and infused through a 0.2 micrometer in-line filter. The IV bag may be constructed of PVC or PO; the IV infusion line may be constructed of PVC or PE; and the 0.2 micrometer in-line filter may be constructed of PES. The prepared solution may be stored at 2°C-8°C or room temperature for up to 8 hours.

8.1.6 Storage and Stability

2°C-8°C (36°F-46°F) Vial contents should not be frozen or shaken and should be protected from direct sunlight.

Stability studies are ongoing.

CAUTION: No preservative is used in atezolizumab; therefore, the vial is intended for single use only. Discard any unused portion of drug remaining in a vial.

8.1.7 Administration

Atezolizumab is administered as an intravenous infusion over 60 minutes. If the first infusion is tolerated, all subsequent infusions may be delivered over 30 minutes. Do not administer atezolizumab as an intravenous push or bolus. No premedication is indicated for administration of Cycle 1 of atezolizumab. Patients who experience an infusion related reaction with Cycle 1 of atezolizumab may receive premedication with antihistamines or antipyretics/analgesics (e.g. acetaminophen) for subsequent infusions.

8.2 Tiragolumab

8.2.1 Tiragolumab Description

Tiragolumab is a fully human IgG1/kappa mAb that binds TIGIT and prevents its interaction with PVR. The blockade of TIGIT by tiragolumab represents a novel strategy for cancer therapy because its mechanism of action is complementary to that of other checkpoint inhibitors, such as anti-PD-L1/PD-1. Consequently, tiragolumab as a single-agent or in combination with anti-cancer therapies, may enhance the magnitude and quality of tumor-specific T-cell responses, which may result in meaningful anti-tumor activity in solid tumors and in hematological malignancies.

8.2.2 Clinical Pharmacology

The PK of tiragolumab was evaluated as a single-agent in the Phase Ia portion and in combination with atezolizumab in the Phase Ib portion of Study GO30103. As of 2 December 2019, preliminary PK data at tiragolumab doses ranging from 2 to 1200 mg every 21 days (Q3W) show that tiragolumab exposures increased approximately doseproportionally with increasing dose levels. Similarly, tiragolumab exposures increased approximately in a dose-proportional manner from 2 to 1200 mg in combination with 1200 mg atezolizumab Q3W. Further, the PK of tiragolumab in combination with atezolizumab appeared to be consistent with the PK of tiragolumab administered as a single-agent. The geometric mean Cycle 1 C_{max} of tiragolumab ranged from 0.771 to 268 µg/mL and geometric mean Cycle 1 AUC₀₋₂₁ ranged from 2.61 to 2880 day · µg/mL for the dose levels 2 to 1200 mg in the Phase Ia portion of the study. Similarly, the geometric mean Cycle 1 C_{max} ranged from 0.582 to 339 µg/mL and geometric mean AUC₀₋₂₁ ranged from 2.60 to 3000 day · µg/mL for tiragolumab dose levels 2 to 1200 mg in combination with atezolizumab. Preliminary population-PK analysis estimated tiragolumab clearance at 0.28 L/day and linear drug elimination half-life at approximately 15 days.

8.2.3 Pharmacokinetics and Drug Metabolism in Animals

Tiragolumab binds to recombinant human and cynomolgus monkey TIGIT at comparable affinity (0.81 and 4.42 nM, respectively) and blocks binding to its high-affinity receptor PVR at comparable 50% inhibitor concentration reduction (IC₅₀) (\pm standard deviation [SD]) values of 2.15 ± 0.38 nM and 0.44 ± 0.06 nM respectively. Tiragolumab does not bind mouse or rat TIGIT. The PK of tiragolumab following a single IV injection to cynomolgus monkeys was evaluated. In summary, all animals developed anti-drug antibodies (ADAs) from Day 10 onward. Up to Day 7 post-dose, prior to the onset of the ADA response, tiragolumab demonstrated biphasic disposition, and PK parameters such as observed maximum observed serum concentration (C_{max}) and area under the concentration-time curve (AUC) from time 0 to 7 days post-dose (AUC₀₋₇) were similar to other IgG1 mAbs against low-expressing targets (Deng et al. 2011). The toxicokinetics (TK) of tiragolumab were evaluated as part of the repeat-dose Good Laboratory Practice (GLP) toxicity studies in cynomolgus monkeys (Study 15-1334 and Study 17-2910). After repeated administration of MTIG7192A in the 1-month study (Study 15-1334), all animals in the 10 and 30 mg/kg dose groups developed a detectable ADA response that led to the loss of exposure in most animals. However, only 1 of 10 animals in the 100 mg/kg dose group developed a detectable ADA response. In the 26-week study (Study 17-2910), 5 of 6 animals in the 30 mg/kg and 5 of 6 animals in the 100 mg/kg dose groups were ADA-positive and had slightly lower MTIG7192A serum concentrations when compared to animals with negative ADA results. In both studies, systemic exposure was maintained in the ADA-negative animals, and the TK profile was consistent with that expected based on the single-dose PK study. The serum concentration-time profiles of all dose groups exhibited apparent biphasic disposition in which a rapid initial distribution phase was followed by a slower elimination phase.

8.2.4 Supplier

Tiragolumab is provided by Genentech.

8.2.5 Dosage Form and Preparation

Tiragolumab (also known as MTIG7192A) is a fully human mAb that binds to TIGIT. The recombinant antibody is produced in Chinese hamster ovary (CHO) cells, and consists of two heavy chains (456 amino acid residues each) and two light chains (220 amino acid residues each). There are two N-linked glycosylation sites (Asn306) in the fragment crystallizable (Fc) domain. Tiragolumab will be supplied as a sterile liquid in a single-use, 15-mL glass vial. The vial contains approximately 10 mL (600 mg) of tiragolumab solution.

Tiragolumab is to be administered by IV infusion either neat or after dilution in 0.9% NaCl. The concentration of tiragolumab is 60 mg/mL. Using this

concentration, calculate the appropriate volume of undiluted study drug according to patient dose and product concentration.

| Tiragolumab dose | Tiragolumab (60 mg/mL, 600 mg) |
|-------------------------|---------------------------------------|
| 120 mg | 2.0 mL* |
| 300 mg | 5.0 mL |
| 420 mg | 7.0 mL |
| 600 mg | 10 mL |
| 840 mg | 14 mL |
| 1200 mg | 20 mL |

* doses must be administered to the gradation on syringes (e.g. 1 mL increments)

The final concentration of drug in the IV bag should be between 0.2 and 12.0 mg/mL. It may be necessary to remove an amount of saline from the IV bag equivalent to the amount of study drug volume to be added.

A 0.2 µm in-line filter must be used with the infusion set during administration. The compatibility of tiragolumab with diluents other than described is unknown.

8.2.6 Storage and Stability

Tiragolumab must be prepared for dosing under appropriate aseptic conditions as it does not contain antimicrobial preservatives. The dose solution should be used immediately. If not used immediately, the total storage time of the dose solution prior to administration should not exceed 24 hours to limit the risk of microbial growth in case of accidental contamination. The recommended storage condition for the drug product and dose solution is 2°C–8°C, but dose solutions may be stored at room temperature for up to a maximum of 4 hours. The compatibility of tiragolumab with diluents other than described is unknown.

8.2.7 Administration

Tiragolumab must not be infused into the same line or cannula concomitantly with other drug infusions, including parenteral nutrition. Infusions of blood products and any electrolyte supplementation must not occur simultaneously with infusion of tiragolumab. A 0.2 micron in line filter must be used with the infusion set during administration.

9.0 CORRELATIVE STUDIES

9.1 Tissue for Whole Exome Sequencing

At least 11 unstained positively charged 5µm slides from resection or shave biopsy plus one contiguous H&E stained slide will be shipped to Natera using the address in Section

9.4. A de-identified copy of the associated pathology report should accompany the tissue specimen.

9.2 Blood for Whole Exome Sequencing

Six mL of blood will be collected into a K2-EDTA tube for whole exome sequencing for development of the Signatera assay during Step 1 screening. Immediately after the draw, thoroughly mix the blood with the anticoagulant by gently inverting the tube 8x. Within 2 hours of draw, the blood will be shipped at ambient temperature with a refrigerated gel pack overnight to Natera using the address in Section 9.4.

9.3 Blood for ctDNA

Twenty mL of peripheral blood will be drawn into 2 pre-labeled circulating tumor DNA BCT tubes (Streck 218962, NAT-800632) at the following time points:

- Step 2 screening (4 to 12 weeks after date of surgery)
- C3D1
- C6D1
- C9D1
- C12D1
- End of treatment (OPTIONAL)

We will follow ctDNA titers longitudinally and correlate level changes with treatment response and/or relapse based on clinical and/or radiographical assessments. Note that ctDNA testing will be discontinued after two consecutive negative tests.

Immediately after blood is drawn, thoroughly mix the blood with the anticoagulant by gently inverting it 8 times. Do not shake vigorously.

Tubes should be shipped to Natera at ambient temperature within 24 hours of collection.

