| Treatment consent | | X | | | | |
| Review of medical record | X | | | | | |
| Confirmation of resection | X | | | | | |
| H&P, PS, wt | | X | X | | X | |
| CBC | | X | X | | | |
| CMP, LDH, amylase, lipase | | X | X | | | |
| TSH, free T3 or total T3, free T4 | | X | X | | | |
| INR, aPTT ⁹ | | X | | | | |
| EBV serology | X ¹¹ | | | | | |
| HIV serology | X ¹¹ | | | | | |
| HBV serology | X ¹¹ | | | | | |
| HCV serology | X ¹¹ | | | | | |
| Pregnancy test ³ | | X | X | | | |
| Urinalysis reflex to micro and/or culture ⁹ | | X | | | | |
| ECG | | X | X ¹² | | | |
| Randomization ⁶ | | X | | | | |
| Blood for ctDNA (Signatera testing) | | X ⁵ | X ⁸ | | X ¹⁰ | |
| Whole blood and tissue for whole exome sequencing (for design of Signatera assay) | X ¹³ | | | | | |
| Atezolizumab | | | X ⁴ | | | |
| Tiragolumab ⁷ | | | X ⁴ | | | |
| CT scan | | X | | X ² | | X |
| AE assessment | | | Baseline through 90 days after last day of treatment | | | |

1. corresponds with the end of every 3rd cycle; if there are treatment delays, imaging should continue to be done every 12 weeks rather than waiting for the end of every 3rd cycle

2. Q12W during Years 1 and 2 after surgery, Q24W during Year 3 after surgery; depending on when a patient discontinues treatment, follow-up may be Q12W or Q24W; follow-up will discontinue after 3 years have elapsed from date of surgery

3. women of childbearing potential only

4. treatment can continue for up to 13 cycles; refer to Section 5.2 for instructions regarding monitoring of vital signs and post-infusion observation

5. must take place 4-12 weeks after surgery; if ctDNA positive, patients will be randomized to receive either atezolizumab and tiragolumab or atezolizumab monotherapy, and if ctDNA negative, patient will not continue in this study

6. stage 1 only; randomization must occur no more than 16 weeks after date of surgery

7. if randomized to receive tiragolumab during stage 1; all patients during stage 2.

8. prior to dosing on C3D1, C6D1, C9D1, C12D1 – the collection of blood for ctDNA should be discontinued after 2 consecutive negative tests

9. required at Step 2 screening and thereafter only as clinically indicated

10. optional

11. may take place up to 42 days prior to C1D1
12. ECG should be performed at Step 2 screening, C3D1, C6D1, C9D1, and C12D1

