10.0 DATA SUBMISSION SCHEDULE

Case report forms with appropriate source documentation will be completed according to the schedule listed in this section. Data may be up to 1 cycle behind at any given time.

| Case Report Form | Submission Schedule |
|--|---|
| Original Consent Form | Prior to registration |
| On-Study Form Medical History Form Treatment Assignment Form | Prior to starting treatment |
| ctDNA Form | Baseline, C3D1, C6D1, C9D1, C12D1, end of treatment |
| Treatment Form | Every cycle |
| Toxicity Form | Continuous |
| Treatment Summary Form | Completion of treatment |
| Follow Up Form | Frequency per study calendar |
| Imaging Form | Baseline, every 12 weeks for the first 2 years after surgery, every 24 weeks for the third year after surgery |
| Recurrence Form | Time of disease recurrence |
| Death Form | Time of death |
| MedWatch Form | See Section 7.0 for reporting requirements |

Any queries generated by Washington University must be responded to within 28 days of receipt by the participating site. The Washington University research team will conduct a regular review of data status at all secondary sites, with appropriate corrective action to be requested as needed.

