14.3 Secondary Endpoints

- Confirmed ctDNA negative rate, defined as the proportion of ctDNA-positive patients having two consecutive negative ctDNA tests.
- Relapse free survival (RFS), defined as the duration of time from the date of positive ctDNA being confirmed to the date of earliest disease relapse or death, whichever occurs first. Patients who neither relapse nor die by the data cutoff date will be censored at the last follow up date.
- Distant metastasis free survival (DMFS), defined as the duration of time from the date of positive ctDNA being confirmed to the date of appearance of a distant metastasis or death, whichever occurs first. Patients who neither develop distant metastasis nor die by the data cutoff date will be censored at the last follow up date.
- Overall survival (OS), defined as the duration of time from the date of positive ctDNA being confirmed to death from any cause. Patients who are alive by the data cutoff date will be censored at the last follow up date.

- Safety and tolerability will be defined as the number of treatment (i.e., atezolizumab and tiragolumab) related grade 3 or greater adverse events (AEs). Adverse events will be assessed using CTCAE v5.0 criteria. Safety will be monitored from the time of initiation of study treatment to 30 days after discontinuation of therapy.

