14.7 Statistical Analyses

Descriptive statistics will be used to summarize the trial results. Statistics for continuous variables may include means, medians, ranges and appropriate measures of variability. Qualitative variables will be summarized by counts and percentages. The uncertainty of estimates will be assessed by confidence intervals (CIs). All analyses will be considered as exploratory, even if statistical tests will be used.

ctDNA clearance and confirmed negative rate, as well as safety data will be summarized by the number and proportions. RFS, DMFS, and OS will be presented via the Kaplan-Meier method. Median survival and corresponding two-sided 95% CIs will be computed. Survival rates with 95% CIs will be estimated. The group survival difference (i.e., treatment vs. reference) will be examined by the log-rank test. Further exploratory correlative analyses will be performed via Fisher exact test, t-test, or nonparametric Wilcoxon–Mann–Whitney test, if needed.

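### Confirmed ctDNA negativity needs two consecutive negatives, but no required sample follows C12D1 or an early stop, so a first negative at the last required test is confirmed only if the optional end-of-treatment draw is done

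*Combined protocol and SAP*

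**What the plan says.** Section 14.3 gives the endpoint as "Confirmed ctDNA negative rate, defined as the proportion of ctDNA-positive patients having two consecutive negative ctDNA tests". Section 2.0 lists it first among the secondary objectives, for both arms.

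Footnote 8 of the Schedule of Activities places the required on-treatment draws "prior to dosing on C3D1, C6D1, C9D1, C12D1". Footnote 10 marks the end-of-treatment (EOT) draw as optional, and Section 9.3 agrees: "End of treatment (OPTIONAL"). The ctDNA row is blank in the follow-up column. Footnote 4 says that "treatment can continue for up to 13 cycles", so treatment runs past the last required draw.

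Section 9.3 adds: "Note that ctDNA testing will be discontinued after two consecutive negative tests". The ctDNA form in Section 10.0 is due at "Baseline, C3D1, C6D1, C9D1, C12D1, end of treatment".

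On analysis, Section 14.7 says only that "ctDNA clearance and confirmed negative rate, as well as safety data will be summarized by the number and proportions". Neither 14.3 nor 14.7 says whether an EOT result can supply the second negative, or how a patient with a single, last, unconfirmed negative is classified.

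**The concern.** A two-test endpoint needs a second test after every possible first negative. Here two groups have no required second test:

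- patients first negative at C12D1;
- patients with one negative who stop treatment before the next draw. Draws are three cycles (12 weeks) apart, so this window is wide.

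For both, success depends on whether an optional sample was taken. With every ctDNA-positive patient in the denominator, those without it would naturally be scored as not confirmed. The result would then partly reflect sampling practice. If early stopping or EOT uptake differs between the arms of this open-label trial, the descriptive picture of the two arms is distorted as well. A sample that was never drawn cannot be recovered at analysis.

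**Working it through.** **The plan's own figures.** The plan states no figure for this endpoint. Its only design calculation is for the primary endpoint: 18 + 25 = 43 patients, continue at 3 or more of 18, promising at 8 or more of 43. It reproduces exactly, with one-sided alpha 0.0480 and power 0.8003 for 10% versus 25%. It uses only the C3D1 test, so the EOT sample does not enter it.

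**Calendar.** C12D1 falls 11 × 28 = 308 days after C1D1, and thirteen full cycles end at 13 × 28 = 364 days. The optional EOT draw is the only sample in the remaining 56 days (8 weeks) or afterwards.

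**Size of the loss.** Under the natural reading,

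loss = P(last required test is an unconfirmed negative) × P(EOT not drawn) × P(EOT would have been negative).

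Assumptions:

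- Negative at C3D1: 10% or 25%, the plan's null and target rates.
- Newly negative at each later test: 5% or 10% (not in the documents).
- Next test negative after a negative: 90% (not in the documents).
- Stopping between consecutive tests: 0%, 5% or 10% (not in the documents).

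**One case in full: 25%, 5%, 90%, 5% stopping.**

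1. After C3D1: negative 0.2500, positive 0.7500.
2. Before C6D1, 0.2500 × 0.05 = 0.0125 stop with one negative. At C6D1, 0.2375 × 0.90 = 0.2138 are confirmed, and 0.7125 × 0.05 = 0.0356 are newly negative.
3. Before C9D1, 0.0018 stop with one negative. At C9D1, 0.0305 are confirmed and 0.0333 are newly negative.
4. Before C12D1, 0.0017 stop with one negative. At C12D1, 0.0285 are confirmed and 0.0302 are newly negative.
5. Confirmed without EOT draws: 0.2138 + 0.0305 + 0.0285 = 0.273.
6. Last negative unconfirmed: 0.0125 + 0.0018 + 0.0017 + 0.0302 = 0.046. Two thirds of this arises at C12D1 and one third from early stops.
7. With every EOT sample drawn: 0.273 + 0.90 × 0.046 = 0.314. At half uptake: 0.293.

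**All cases** (percent; the loss is computed before rounding):

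| Negative at C3D1 | Newly negative per test | Stop between tests | Unconfirmed last negative | Confirmed, no EOT | Confirmed, half EOT | Confirmed, all EOT | Loss, no EOT |
|---|---|---|---|---|---|---|---|
| 10 | 5 | 0 | 4.1 | 16.9 | 18.8 | 20.7 | 3.7 |
| 10 | 5 | 5 | 4.5 | 15.5 | 17.5 | 19.5 | 4.0 |
| 10 | 5 | 10 | 4.8 | 14.2 | 16.4 | 18.5 | 4.3 |
| 10 | 10 | 0 | 7.5 | 24.5 | 27.8 | 31.2 | 6.7 |
| 10 | 10 | 5 | 7.7 | 22.2 | 25.7 | 29.1 | 6.9 |
| 10 | 10 | 10 | 7.9 | 20.0 | 23.6 | 27.2 | 7.1 |
| 25 | 5 | 0 | 3.5 | 29.2 | 30.8 | 32.4 | 3.2 |
| 25 | 5 | 5 | 4.6 | 27.3 | 29.3 | 31.4 | 4.2 |
| 25 | 5 | 10 | 5.7 | 25.4 | 28.0 | 30.5 | 5.1 |
| 25 | 10 | 0 | 6.4 | 35.6 | 38.4 | 41.3 | 5.7 |
| 25 | 10 | 5 | 7.4 | 32.9 | 36.2 | 39.5 | 6.6 |
| 25 | 10 | 10 | 8.4 | 30.3 | 34.1 | 37.9 | 7.6 |

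With no EOT draws the loss runs from 3.2 to 7.6 points, or about 1.4 to 3.2 of 43 combination patients. At half uptake it is 1.6 to 3.8 points. A single patient is 1/43 = 2.3 points in the combination arm and 1/18 = 5.6 points in the reference arm.

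**Limits of the model.** Positive and negative patients stop at the same rate, and an EOT draw is treated like any scheduled test although it may follow sooner. Recurrence ends treatment (Sections 5.6 and 6.2.1), and Section 1.2 reports that most patients with detectable ctDNA in its cited study relapsed within a year of surgery. Patients still positive at C9D1 are therefore the likeliest to have left, which would reduce the number first negative at C12D1.

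**The case against.** **It can be confirmed.** A reader might infer that a first negative at C12D1 can never be confirmed. The documents do not support that. The EOT visit exists, the draw is offered and the form has a place for the result. The gap depends on uptake, about which the documents say nothing, including whether the site or the patient decides.

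**Bias is not automatic.** A reader might also infer that the rate must be biased downward. Section 14.3 counts patients who have two negatives, and a patient with one does not meet that definition. The understatement is relative to a schedule that gives every first negative a second test, and it assumes that unconfirmed counts as failure, which the plan does not state. Dropping such patients from the denominator would give 27.3 / (100 − 4.6) = 28.6% in the worked case, against 31.4% with full sampling. Testing also stops after two negatives, so a later return to positive goes unseen. As a measure of sustained clearance, the rate could err upward. That objection concerns durability, which is a different question. Under the endpoint as defined and the natural reading, a missing confirmatory draw can only lose successes.

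**The form schedule is not a contradiction.** A form slot at end of treatment is needed even for an optional sample.

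**The stakes are modest.** Section 14.7 calls all analyses exploratory, and Section 14.1 rules out a formal efficacy comparison between the arms.

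These points limit the direction and weight of the concern. They leave standing that a secondary endpoint depends on discretionary sampling and that no rule covers an unconfirmed last negative.

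**Conclusion.** The point holds in conditional form. No required ctDNA sample follows C12D1 or an early stop, so patients whose first negative is their last required test are confirmed only if the optional EOT sample is drawn. If the remainder count as not confirmed, the descriptive rate is understated by about 3 to 8 percentage points at zero uptake, about 2 to 4 at half uptake, and not at all at full uptake. The range rests on assumed later-clearance, confirmation and stopping rates that the documents do not supply. The understatement could differ between arms, but nothing in the documents shows that it will.

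The share of patients left with an unconfirmed last negative (3.5% to 8.4% in the table) should not be read as the loss itself. It becomes the loss only after multiplying by the chance that the EOT sample is missed and the chance that it would have been negative.

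The primary endpoint, the stage 1 rule and the final rule are untouched. This is a worthwhile, low-cost improvement to a secondary endpoint and no threat to the trial's main conclusion.

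**What to change.** 1. In footnote 10 of the Schedule of Activities and in Section 9.3, require the EOT ctDNA draw, including after early discontinuation, for any patient whose most recent ctDNA test was a first negative. Leave it optional for everyone else.
2. In Section 14.3, state that an EOT result counts toward the two consecutive negatives, and that a last negative still unconfirmed counts as not confirmed.
3. In Section 14.7, add a sensitivity analysis for those patients, for example counting them as confirmed to give an upper bound, and report their number by arm.
4. Annotate the ctDNA form entry in Section 10.0 to match.

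**Cost.** Applying the table's rates to all 61 treated patients, 3.5% to 8.4% would need the draw: 2.1 to 5.1 assays, early stoppers included. If later clearance were as high as 20% per test, with 10% negative at C3D1 and no stopping, first negatives at C12D1 alone would be 0.90 × 0.80² × 0.20 = 11.5%, or 7.0 of 61. A fair budget is therefore roughly 2 to 7 assays for first negatives at C12D1, plus some for early stoppers, at a visit already in the schedule. The change affects blood sampling only, not treatment.
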